Low-intensity versus high-intensity home-based treadmill training and walking attainment in young children with spastic diplegic cerebral palsy

NCT #: NCT02424526

Date: 7/29/2014

Study Protocol and Statistical Analysis Plan

Study Design

This is a prospective randomized controlled study which will include 24 pre-ambulatory children with CP under 3 years of age (i.e. up to the child's third birthday), GMFCS levels I and II.

Study Sites

All assessments and interventions will be conducted at the children's homes. In order to achieve a culturally and ethnically diverse sample, children will be enrolled at three sites in two US states. [name] will enroll children at the Seattle, WA site, [name] will enroll children at the Tacoma, WA site and [name] will enroll children at the Sacramento, CA site. Seattle, WA has a relatively high-income White (non-Hispanic descent) and Asian urban population; Tacoma, WA has a relatively lower-income White, Black and Hispanic urban population; Sacramento, CA has a relatively middle-income Hispanic, Black and Asian urban and rural population.²³ Conducting the study at these 3 sites will enable us to better generalize the results to a larger population.

Participants and Characteristics

24 pre-ambulatory children with CP under 3 years of age, GMFCS levels I and II, with bilateral impairment, who show signs of walking readiness will be recruited at the 3 different study sites. Eight children will be randomly assigned to a low-intensity or a high-intensity treadmill training group at each site.

Inclusion criteria will include

- Signs of walking readiness as demonstrated by the ability to sit for 30 seconds when placed and to take 5 to 7 steps when supported at the trunk or arms. These criteria were used in previous research to assure that the children had sufficient trunk control and bipedal control for the treadmill intervention.¹⁷ Children will be pre-ambulatory and will not engage in regular ambulation with an assistive device outside of physical therapy.
- Because young children often are not formally diagnosed with CP until 2 years of age, we will include children
 - who show bilateral symmetrical or asymmetrical impairment (i.e. diplegia and quadriplegia, but not hemiplegia)
 - who demonstrate upper motor neuron signs (i.e. spasticity and/or hyperreflexia)
 - who have been identified as high-risk for a motor disability by a physician

Exclusion criteria will be

- a history of uncontrolled seizures

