Due to their young age, some of the children, particularly those in the high-intensity group, might have difficulty maintaining attention to the task during the intensive intervention. In order to keep them motivated during the treadmill walk, the treadmill will be placed in front of a TV or laptop showing an age-appropriate movie chosen by their parents. This technique has proven to be helpful in previous studies and has the added benefit of preventing the children from looking downward.^{17,20} In one previous study, the average daily time walked on the treadmill was 28.2 ± 11.2 minutes for the twice daily walking periods by a similar group of children using the above described motivational techniques.¹⁷

Some children might be unable or unwilling to hold onto the handle bars of the treadmill. In this case, a second parent will be necessary to help the child maintain grip of the handle bars. If a second person is not available, the child's hand can be loosely strapped onto the handle bar for the duration of the walk.

Outcome Measures

Each child will be tested at pre-intervention, post-intervention, at 1-month and at 4-months following the intervention.

Valid and reliable outcome measures at the *Body Structures and Functions Level* of the International Classification of Functioning, Disability and Health (ICF) Model²⁸ will include the 1-minute Walk Test. Outcome measures at the *Activity Level* of the ICF model will include the Gross Motor Function Measure-66 (GMFM-66), Peabody Developmental Motor Scales-2 (PDMS-2), Functional Mobility Scale (FMS), the Timed 10-meter Walk Test and the StepWatch accelerometer. Outcome measures at the *Participation level* of the ICF Model will be the Pediatric Evaluation of Disability Inventory Mobility Scale (PEDI). Videotapes of assessments will be scored by an assessor blinded to group allocation for the GMFM and PDMS-2.

- 1-minute Walk Test: The child's walking distance will be measured in meters over 1 minute at their self-selected walking speed if the child is able to walk with an assistive device. The 1-minute Walk Test is a reliable test of walking endurance in young children with CP, when administered after a practice trial. Due to the young age and early ambulatory status of the children, the 1-minute Walk Test is more appropriate than a 6- minute Walk Test.²⁹

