- GMFM-66: The child's gross motor skills related to rolling, sitting, crawling, standing and walking will be assessed by observation. This measure is criterion-referenced and design to track progress over time in children with cerebral palsy. The GMFM is considered the gold standard for the assessment of children with CP and has excellent validity, reliability and sensitivity to change in young children.^{3,30}
- PDMS-2: The child's gross motor skills compared to children with typical development are assessed by observation. This measure is norm-referenced and determines the amount of developmental delay in a child compared to typically developing children. The PMDS-2 is used widely and shows excellent responsiveness to change over time.³¹
- FMS: This scale is used to document the child's current mobility level and the amount required for walking at different distances. It is designed to rate a child's walking ability over household, classroom and community distances. Children are rated on a Likert scale from 1 to 6 with 1 being the lowest ranking (uses wheelchair) and 6 being the highest ranking (independent on all surfaces). The FMS has been found to reliably measure the amount of support needed for walking in children with CP.^{32,33}
- Timed 10 meter walk test: The child's walking speed will be recorded over 10 meters if the child is able to walk with an assistive device. The timed 10MWT has shown to be most reliable in young children when they are encouraged to walk at a fast speed rather than a self-selected speed.³⁴ The children will be motivated to walk at their fastest speed when administering this test.
- PEDI: The PEDI is a valid and reliable tool that provides an assessment of a child's functional status and performance.³⁵ This is a parent questionnaire regarding their child's mobility needs. The Mobility Scale of the PEDI will be used, which is based on parent report and observation.

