[name] will recruit from local early intervention providers (including Birth to Three Developmental Services, A Step Ahead in Pierce County, and Tacoma Learning Center), Mary Bridge Children's Hospital, the Children's Therapy Unit, and from Washington Pediatric Special Interest Group. [name] has successfully recruited subjects from these sites previously.

No problems with recruitment of study participants are anticipated due to each investigator's connections in their local medical community. If one of the sites should fall short of qualified children, more children could be covered at one of the other sites. Drop-out rates are expected to be low due to the home-based nature of the study. All of the outcome measures as well as the intervention will be conducted at the children's homes. It is possible that a young child might fall sick for any of the planned visits by the PIs, or might not fully participate in one of the visits for other reasons. In this event, the PI will reschedule a repeat visit within a few days of the original visit to collect the data.

Between the three sites, twelve children will receive high-intensity treadmill training and twelve children will receive low-intensity treadmill training. Due to the stringent inclusion and exclusion criteria, the children in the two groups are expected to show no significant between-group differences at baseline. In [name] previous study on home-based treadmill training, group allocation using the same criteria led to two groups with no significant differences regarding age and developmental skills.¹⁷

Power Analysis

Power analysis was conducted to determine a sample size based on developmental data and based on StepWatch data.

To examine the optimal dosing for walking attainment, a projected sample size of 18 subjects (9 per group) at 95% power was calculated from Peabody Developmental Motor Scales-2 Locomotion subscale change scores from [name] previous home-based treadmill training study (n=12; GMFCS levels I and II; ages 15-32 months)¹⁷. An additional 6 subjects will be added to strengthen the study design and allow for possible attrition, leading to a total number of 24 subjects.

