Outcome measures at the *activity level* of the International Classification of Functioning, Disability and Health (ICF) Model will include the Gross Motor Function Measure (GMFM), Peabody Developmental Motor Scales-2 (PDMS-2), Functional Mobility Scale (FMS), the Timed 10-meter Walk Test, the 1-minute Walk Test and the StepWatch accelerometer. Outcome measures at the *participation level* of the ICF Model will be the Pediatric Evaluation of Disability Inventory Caregiver Mobility Scale (PEDI). Videotapes of assessments will be scored by an assessor blinded to group allocation for the GMFM and PDMS-2. StepWatch data will be collected for all awake daytime hours over a 7 day period at study onset before treadmill training commences and at each of the post-intervention assessments. The StepWatch monitor will be secured around the child's ankle with a small knit cuff. [name] has successfully employed this method of monitor attachment in toddlers with and without motor limitations.^{23,36} StepWatch outcomes will be average number of strides/day and the percentage of the time walking.

[figure not shown]
In order to address specific aim # 1 (optimal parameters for dosing home-based treadmill training by comparing high-intensity to low-intensity treadmill training) and specific aim # 2 (effects of high- versus low-intensity treadmill training on walking attainment and overall walking activity), between-group differences of all the outcome measures will be analyzed as described in the next section. Specifically, between-group differences in GMFM and PDMS-2 will examine the effects of dosage on walking attainment and skills related to standing and walking. The changes in support needed for walking will be measured by the FMS in the two groups. Differences in walking speed and walking endurance will be analyzed using the data from the Timed 10-meter Walk Test and the 1-minute Walk Test, respectively. The parent perspective on overall child mobility will be analyzed by using the PEDI. Finally, overall walking activity will be shown by between-group differences from the StepWatch data.

Data Analysis

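### The two timed walk tests are recorded only for children who can walk with a device, yet both enter a four-visit ANOVA with no rule for a child who cannot

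*Combined protocol and SAP*

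**What the plan says.** Under Outcome Measures, the 10-meter test is conditional: "The child's walking speed will be recorded over 10 meters if the child is able to walk with an assistive device". The 1-minute test measures distance "at their self-selected walking speed if the child is able to walk with an assistive device". The visit schedule includes a baseline: "Each child will be tested at pre-intervention, post-intervention, at 1-month and at 4-months following the intervention".

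The inclusion criteria under Participants and Characteristics state: "Children will be pre-ambulatory and will not engage in regular ambulation with an assistive device outside of physical therapy".

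Methodology gives both tests a between-group role: "Differences in walking speed and walking endurance will be analyzed using the data from the Timed 10-meter Walk Test", with the 1-minute test serving for endurance. Specific aim 2 in the same section concerns the "effects of high- versus low-intensity treadmill training on walking attainment and overall walking activity".

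Data Analysis lists both tests among the parametric variables for the repeated-measures ANOVA, with alpha 0.05.

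Two provisions come near the issue. Enrollment procedures allows a repeat visit within a few days if a child is sick or "might not fully participate in one of the visits for other reasons". Methodology excludes the data of a child whose parent cannot learn to train safely. Neither deals with a child who attends, cooperates and cannot walk. The FMS, by contrast, has a score at its lowest level for a child who uses a wheelchair.

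**The concern.** A repeated-measures ANOVA needs a value at each visit, or a stated way of doing without one. Here a value may be absent because of the very limitation that defines the population. The plan gives no score for inability, no analysis set and no alternative method, so the analyst must choose between two handlings that answer different questions.

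- **Complete cases.** Only children able at all four visits are kept, so baseline ability caps the number.
- **Available values.** At each follow-up, the children who can walk by then are compared. Walking attainment is an effect that aim 2 sets out to study, so equal ability in the two arms cannot be assumed.

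At stake are the walking-speed and walking-endurance comparisons, which the plan assigns to these two tests. Preliminary analyses for a conference are also planned, so the choice could be made after data have been seen.

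**Working it through.** **1. Inputs.** From the documents: 24 children, 12 per arm, 4 per arm at each of three sites; four visits; alpha 0.05. The documents do not give the proportion able to do the tests, the SD of speed or distance, or the way treatment acts. These are assumed below and varied.

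**2. The plan's own figure.** No power or sample size is stated for either walk test. The stated 18 children (9 per group) come from PDMS-2 Locomotion change scores with effect size 1.87 and 95% power. A two-sample t-test (noncentral t, two-sided alpha 0.05, sidedness assumed) gives power 0.935 with 8 per arm and 0.961 with 9. The figure reproduces, and this point does not touch it.

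**3. Complete cases.** Let p be the proportion able at baseline. Expected retention is at most 24p. The number kept per arm is at most Binomial(12, p), so the chance that at least one arm keeps fewer than 2 is at least 1 - P(X ≥ 2)².

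| p | 24p | Chance an arm keeps fewer than 2 (at least) |
|---|---|---|
| 10% | 2.4 | 1 - 0.341² = 88% |
| 20% | 4.8 | 1 - 0.725² = 47% |
| 50% | 12 | 1 - 0.997² = 1% |
| 90% | 21.6 | 0% |

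On a simple t-test, the difference detectable with 80% power is 1.20 SD with 12 per arm, 1.80 SD with 6 and 3.07 SD with 3.

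Baseline ability precedes training. If no able child later loses the ability, the retained set is a subgroup defined before treatment, and high versus low intensity within it is still a randomized comparison.

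**4. Available values at one follow-up.** Let latent ability be standard normal in the low-intensity arm. A child walks if ability exceeds c = Φ⁻¹(1 - p), where p is now the proportion of the low arm able. Write λ(x) = φ(x)/(1 - Φ(x)).

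- **A. One latent ability drives both walking and speed, shifted by 1 SD.** Walkers-only difference = 1 + λ(c - 1) - λ(c).
- **B. Treatment adds 1 SD of speed, ability equal in both arms.** Difference = 1.
- **C. Treatment only brings more children into walking, and no child's speed changes.** Difference = λ(c - 1) - λ(c).

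Example with p = 60%: c = -0.253, λ(c) = 0.644, λ(c - 1) = 0.203. A gives 1.203 - 0.644 = 0.56. C gives 0.203 - 0.644 = -0.44.

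| Low arm able | High arm able (A, C) | A (SD) | B (SD) | C (SD) |
|---|---|---|---|---|
| 20% | 56% | 0.30 | 1.0 | -0.70 |
| 40% | 77% | 0.43 | 1.0 | -0.57 |
| 60% | 89% | 0.56 | 1.0 | -0.44 |
| 80% | 97% | 0.73 | 1.0 | -0.27 |
| 90% | 99% | 0.83 | 1.0 | -0.17 |

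**5. What the alternatives can deliver.** The four-visit ANOVA cannot be simulated without a handling rule, so a single-visit walkers-only t-test stands in for it. It is set against a site-stratified rank test (van Elteren) on all 24 children with inability scored 0. Power for a 1 SD effect at 20/40/60/80/90% of the low arm able:

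- A: walkers-only 4/13/28/45/54%; zero-scored 48/55/57/59/60%.
- B: walkers-only 8/25/40/53/60%; zero-scored 5/7/12/26/41%.
- C: zero-scored about 26/17/7/6/6%.

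The type I error of the rank test is 4.6% to 5.3%. Neither test is better under every mechanism.

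The proportion able is imprecise: 9/12 v 5/12 is a 33-point difference with a Newcombe 95% interval of about -5 to 61 points.

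**The case against.** The strongest reply is that complete-case analysis, though small, is sound. It keeps only children able before training began, and if they stay able it compares randomized arms within a baseline-defined group. This stands. A reader might infer that any handling of these tests breaks the randomization. The documents do not support that: selection on an outcome that treatment may change belongs to the available-value handling. It would enter complete cases only if ability were lost differently in the two arms.

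A reader might also infer that no child can be tested at baseline, or that both tests should leave the ANOVA with no walkers-only comparison at all. The first goes too far, because the criteria exclude only regular device walking outside physical therapy. The second would discard an unbiased test with 53% to 60% power under mechanism B when 80% to 90% can walk.

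It is also fair to say that every proportion and mechanism here is assumed, that the SD figures fix neither the size nor the direction of any harm, and that GMFM, PDMS-2 and FMS cover walking skill and support in all children. These points limit the weight of the concern. They do not supply the missing rule, and a rescheduled visit a few days later does not help a child who cannot yet walk.

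**Conclusion.** The concern holds for the two timed walk tests. It is certain from the text that recording depends on walking ability and that no rule covers inability. The consequence depends on the handling chosen. Complete cases mainly lose sample and generality, severely if few children are able at baseline and little if 90% are. Available values compare children selected on attained walking, and these tests alone cannot show whether the difference is unbiased, too small or reversed. The distortion is nil under mechanism B and shrinks as nearly all children become able. The sample size, PDMS-2, GMFM, FMS and StepWatch are not affected. This should be settled before data are analysed, but it is confined to the speed and endurance comparisons.

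**What to change.** Amend Methodology (the paragraph on specific aims and measures) and Data Analysis together, so that they do not conflict:

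1. At each visit, record a reason code when a walk test is not done: unable, refused or ill.
2. Report the proportion able to do each test, per arm and visit, on all randomized children with 95% intervals, as the all-randomized result for these tests.
3. Keep any comparison of speed or distance among walkers as secondary. Label it as conditional on ability and not a comparison of the randomized groups, state the number analysed per arm, and read it beside the proportion able, FMS, GMFM and PDMS-2.

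Optionally, add a rank comparison of all randomized children with inability scored as 0 m or 0 m/s, at one visit named in advance. State that it mixes ability with speed, and that its power is low if treatment changes only speed or, when most children can already walk, only ability.

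The cost is one form item and some analysis wording, with no extra visits or children. The drawbacks are that the proportion able is imprecise with 12 per arm and that the walkers-only result carries less weight.

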To assure sufficient power to assess the effects of treadmill training on overall walking activity, a proposed sample size of 12 per group would have 80% power to detect a 3000 stride/day difference in treatment intensity as measured with the StepWatch monitor. This is based on [name] cross-sectional StepWatch average stride/day data from 17 youth with CP ages 2-3 years where the mean difference between GMFCS level I and II was 3000 strides.¹⁸

[figure not shown]

Fig. 4. Power analysis for sample size ($\alpha = 0.0$; Power= 0.95; Effect size=1.87; Sample size=18)

Methodology

Approval from the University Institutional Review Board was submitted on July 10, 2014 and approved on July 29, 2014 by the lead institution at California State University, Sacramento. A cooperative agreement will be put in place prior to study onset with the other institutions (please see attached). Due to the children's young age, written informed consent will be obtained from the parents. Parents will be asked to commit to a 6-week stretch uninterrupted by vacations or breaks. Study participation will be discussed and scheduled carefully with the families to allow for 6 weeks of uninterrupted intervention period. Due to the nature of the home-based administration of the intervention by parents and caregivers, high adherence to the study protocol is expected. Investigators will schedule weekly home visits and all assessments at a mutually agreed upon time that is convenient for the families.

After consenting to study participation, the parents for each child will fill out a parent questionnaire containing demographic and health information about their child. A physician form will also be signed prior to study onset to seek medical clearance for the child for the intervention. Group allocation will be determined by blinded drawing from a hat until each of the three study sites has reached a total of 4 children in each group. In the unlikely event that one site might have difficulty with subject recruitment, additional children will be enrolled at another study site.

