A one-way analysis of variance (ANOVA) with repeated measures will be used for comparison of treatment groups for parametric dependent variables, i.e. PDMS-2, GMFM, Timed 10-meter Walk Test, and 1-minute Walk Test. Analysis for non-parametric data for dependent variables, i.e. PEDI and FMS, will be conducted using the Friedman test for comparison between groups. StepWatch data will be examined with the Wilcoxon sign rank test for paired data. Post hoc tests will be performed where appropriate. Alpha will be set at 0.05. In addition, data on whether children reached the minimum clinically important change will be reported for the GMFM.³⁷

[figure not shown]
Study Timeline

Overall Study Timeline

Study recruitment will commence as soon as all study sites have signed the cooperative IRB agreement. All equipment will be ordered immediately after the receipt of the grant. Training on StepWatch use will be conducted by [name] at Seattle Children's Research Institute. [name] and [name] will participate. During the same meeting, reliability training will be conducted on other outcome measures. Recruitment and enrollment will commence immediately by distributing study information at the three sites. It is anticipated that there will be coinciding intervention and data collection for the 8 children at each site for the duration of 15 months. Two treadmills will be available at each site for the 6-week treadmill intervention periods for each child. Video review will be ongoing by the consultant, who is blinded to group allocation, as the videos become available for each child. Preliminary data analysis will be conducted in order to present initial results at conference within the grant period. Once all data is collected, there will be a second on-site meeting of the three PIs in order to assure consistent data entry and to allocate the responsibilities for study result dissemination. All three investigators will engage in manuscript preparation with [name] as first author. Data analysis will be performed by a statistician at the lead institution in collaboration with the PIs. Manuscript preparation will be conducted in the final two months of the 24-month study period.

Study Timeline for Each Subject

As indicated above, each child will be enrolled in the study for a total period of 26 weeks.

Human Subjects

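### Entry criteria are relied on for baseline balance and age enters neither the allocation nor the analysis, so a chance age difference between two arms of 12 would go unadjusted

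*Combined protocol and SAP*

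**What the plan says.** All of this is in the combined protocol and SAP.

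- **Baseline balance.** Enrollment procedures: "Due to the stringent inclusion and exclusion criteria, the children in the two groups are expected to show no significant between-group differences at baseline". In support, it reports that in an earlier home-based treadmill study "group allocation using the same criteria led to two groups with no significant differences regarding age and developmental skills".
- **Arms and allocation.** "Between the three sites, twelve children will receive high-intensity treadmill training and twelve children will receive low-intensity treadmill training". Methodology: "Group allocation will be determined by blinded drawing from a hat until each of the three study sites" has four children in each group. Age plays no part in the draw.
- **Age range.** Study Design admits "24 pre-ambulatory children with CP under 3 years of age" and sets no lower age limit. Power Analysis describes the earlier sample as "n=12; GMFCS levels I and II; ages 15-32 months".
- **Analysis.** Data Analysis: "A one-way analysis of variance (ANOVA) with repeated measures will be used for comparison of treatment groups for parametric dependent variables", namely PDMS-2, GMFM and the two walk tests. For PEDI and FMS, the analysis "will be conducted using the Friedman test for comparison between groups". StepWatch data get a Wilcoxon signed-rank test. No covariate, age-adjusted analysis or sensitivity analysis is named.
- **Scaling of the two motor scales.** Outcome Measures describes GMFM-66 as criterion-referenced and PDMS-2 as norm-referenced. The type of PDMS-2 score to be analysed is not stated.

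**The concern.** The reason given for expecting balance does not support it. Entry criteria narrow the population, but within that population the arms are still two random groups of 12, and their mean ages will differ by chance. The earlier study is weak reassurance, because a non-significant difference among 12 children says little about how close the groups were.

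The plan itself treats age as a variable on which balance matters, since it cites the earlier study on that point. Yet age is used in neither the draw nor the model. If older and younger toddlers gain motor skill at different rates, an age gap that happens to arise would be mixed into the estimated effect of training intensity. Leaving age out would also forgo whatever precision it could supply in a trial of 24.

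**Working it through.** **1. The plan's own figure.** Power Analysis and its figure give effect size 1.87, power 0.95 and N = 18. A two-sample t-test (noncentral t, two-sided alpha 0.05 assumed) has power 0.935 at 8 per group and 0.961 at 9 per group. So 9 per group is the smallest size reaching 0.95, and the stated 18 is reproduced. At the planned 12 per group, power is 0.992.

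**2. Chance gap in mean age.** The documents give no age SD. From the 15 to 32 month span of the earlier sample (17 months), I assume 17/4 = 4.25 (range over four) to 17/√12 = 4.91 (uniform). Site blocking is ignored; it would narrow the limits slightly if ages differ by site.

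SE = SD × √(2/12); 95% limit = 1.96 × SE; typical absolute gap = SE × √(2/π).

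| Age SD (months) | SE | 95% limit | Typical gap | P(gap ≥ 3 months) |
|---|---|---|---|---|
| 3 | 1.22 | ±2.4 | 1.0 | 1% |
| 4.25 | 1.74 | ±3.4 | 1.4 | 8% |
| 4.91 | 2.00 | ±3.9 | 1.6 | 13% |
| 6.93 (uniform 12–36) | 2.83 | ±5.5 | 2.3 | 29% |

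The first and last rows are sensitivity values with no basis in the documents.

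**3. How much the earlier study reassures.** Assume its 12 children were split 6 and 6. The smallest significant age gap is t(0.975, 10 df) × SD × √(2/6), which is 5.5 months at SD 4.25 and 6.3 months at SD 4.91. Power to detect a true 3-month gap was 20% and 16% respectively.

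**4. Effect of an imbalance on the unadjusted comparison.** Let r be the correlation of age with the analysed outcome (not in the documents). A gap at the 95% limit shifts the arm difference by r × 1.96 × √(2/12) outcome SDs:
- r = 0.3: 0.24 SD, which is 13% of 1.87. Conditional type I error is about 8%.
- r = 0.5: 0.40 SD, which is 21% of 1.87. Conditional type I error is about 13%.

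At a gap of one SE, conditional type I error stays at about 5% for both values of r.

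**5. Precision with age in the model.** The variance ratio, adjusted to unadjusted, allowing for the estimated covariate, is (1 − r²) × 21/20. It equals 1 when r² = 1/21, that is r = 0.218. Power is for 12 per group.

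| r | Variance ratio | Change in variance | Power at d = 1.0 |
|---|---|---|---|
| unadjusted | 1 | – | 65% |
| 0 | 1.050 | +5% | 63% |
| 0.2 | 1.008 | +1% | 64% |
| 0.3 | 0.956 | −4% | 67% |
| 0.5 | 0.788 | −21% | 75% |

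The value d = 1.0 is illustrative and is not a planning figure of the trial. At d = 1.87, power is about 99% without adjustment.

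**The case against.** **An unadjusted randomised comparison is valid.** This stands. The draw is random within site, the test keeps its error rate over repeated randomisations, and no analysis depends on the sentence about expected balance. What is left is bias conditional on the imbalance that occurs, and precision.

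**The repeated measures include a pre-test.** This stands in part. A group-by-time or change comparison deals with a difference in starting level. It does not deal with a rate of gain that depends on age.

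**PDMS-2 is norm-referenced.** If age-standardised scores are analysed, part of the age effect is already removed for that outcome. The score type is not stated, and the same cannot be said of the criterion-referenced GMFM-66.

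**The age correlation may be small.** This stands. Every child must be pre-ambulatory, sit for 30 seconds and take five to seven supported steps, so children enter at a similar motor stage whatever their age. Below a correlation of about 0.22, adjustment slightly reduces precision.

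**Stronger readings.** A reader might infer that the dose comparison is biased by design, or that a gap of several months should be expected. The documents support neither: randomisation rules out the first, and the typical gap is about 1.5 months. Nor does Data Analysis specify baseline significance tests, so the plan cannot be faulted for false positives among them.

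**Conclusion.** The point holds as a modest one. The stated reason for expecting balance is unsound, the earlier study is too small to make up for it, and age is handled in neither allocation nor analysis. Under an assumed age SD of 4.25 to 4.91 months, a gap of 3 months or more would arise in about 8% to 13% of such trials. Only near the 95% limits, and with a correlation of 0.3 or more, would the conditional distortion become material.

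A reader might also infer that the trial is underpowered without age adjustment. The plan's own figures do not show that. The precision argument has force only if the true effect is well below 1.87 and age is a reasonable predictor of the analysed outcome. Both the age SD and the correlation are assumptions.

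**What to change.** In the between-arm model for PDMS-2 and GMFM (group-by-time or change), pre-specify baseline age as a continuous covariate, used whatever imbalance is observed. Fixing this in advance avoids a choice made after seeing the data. The model has to be written with an explicit between-arm term, since the one-way wording leaves no clear place for a child-level covariate. State also which PDMS-2 score is analysed, because that determines how much age effect remains.

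Replace the sentence in Enrollment procedures with a statement that baseline characteristics will be described by arm and that the comparison is adjusted for age. The Friedman and signed-rank tests take no covariate, so this change does not reach PEDI, FMS or StepWatch.

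**Cost:** revised SAP text and one degree of freedom. Variance rises by about 5% if age turns out to be unrelated to the outcome. No new data are needed: age is required for eligibility, and the Human Subjects section already lists it among the items to be reported.
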